3.3.5 Analysis

Once the supporting staff collects the data from survey participants, data entry will be carried out. In order to reduce the errors during the data entry, there will be cross checking of entered data by the project coordinator. The patient-physician relationship score from the questionnaire will be calculated into patient-physician relationship percent score.

Exploratory analysis will be done to clean the data by finding the missing values, outliers, and distribution of variables. Analysis will include descriptive analysis, independent T-test for continuous variables, Chi Square (χ^2) test for dichotomous variables, bivariate linear regression analysis and multivariate linear regression analysis.

4. Timeline

The proposed pilot project is planned to run for fourteen months, starting from June 2015 until August 2016. The physician leadership development program will be conducted for two months in the month of September and October 2015. The evaluation process will be conducted in three different duration, for baseline (O_0) and follow-up (O_1), (O_2) assessments (Appendix 5).

5. Budget

The total budget is estimated to be six million seven thousand eight hundred Armenian Drams (6,007,800.00 AMD) to implement this grant proposal (Appendix 6). The estimated budget for this grant proposal is calculated based on optimal fixed and overhead costs. The office and classroom for the program implementation, the classroom of 18 seating capacity is considered as an optimal. The rents are calculated as per AUA facilities' rental fees.⁴⁰ The costing is calculated for this proposal according to the average salaries for the personnel and type of services performed paid in the Armenian market as per May 2015.

6. Ethical Considerations

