3.2 Implementation Plan Synopsis

3.2.1 Program

We proposed to implement the Physician Leadership Development Program to the family physicians of Heratsi polyclinic, which is under the administration of Yerevan State Medical University. During the program, the core training personnel will consist of two physicians who have taken “training of trainers” course. These physician trainers should have a Master of Public Health (MPH) degree from the American University of Armenia. The trainers will take the free online course “Edward Jenner Program” provided by Leadership Academy in National Health Services, United Kingdom.³⁴ The trainers will complete the course and obtain a certificate. On completion of the online program, the trainers will use these materials to teach the family physicians. The trainers will also translate the online program materials into Armenian. The training course includes topics not only about the leadership (as a core component), but also about cooperation, planning, resource management, innovation in patient care, assessment of outcomes of patient care and decision-making.

The program consists of 21 sessions (each 40 minutes), three sessions a week in a seven-week period. The physicians in the primary health centers work on two shifts; Morning shift: (9:00 AM -1:00 PM) and afternoon shift (1:00 PM - 5:00 PM) for six days a week. Each physician has his/her schedule on even and odd days of the week. Separate sessions will be offered to two cohorts on even and odd days of the week. The session will conduct on each day of the week from 2:00 PM until 3:30 PM with a break of fifteen minutes. No session will schedule for Sundays. The sessions will be conducted at the American University of Armenia.

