Response options have nine levels of agreement with each statement from “Strongly Disagree” to “Strongly Agree.” The patient-physician relationship score is the numerical continuous variable, which is a dependent variable. In the self-administered survey questionnaire, the socio-demographic questions refer to sex, age, marital status, socio-economic status, and educational status. The self-administered questionnaire will take about 10 minutes to complete and provides anonymity. To preserve the anonymity, no personal identification information will be collected. Instead, each questionnaire will have a special identification number. The special identification number will consist of six characters. The first character of the identification number will feature one English alphabet, i.e. “H” or “M”. Latter is to represent the polyclinic where the survey participant took the survey. The second character of the identification number will feature one Arabic number, i.e. “0” or “1” or “2”. The numbers “0” represent the baseline assessment and, “1” and “2” represent two follow-up assessments respectively. The other four characters of the identification number will feature Arabic numbers, which will be the numbers of the survey participant. For example, if

“H20604” is the special identification number on the questionnaire, then it implies that the survey participant is from Heratsi polyclinic, who took the survey in second follow-up assessment as 604th participant.

The self-administered survey questionnaire was translated from English into Armenian by two different certified translators and later both copies of the Armenian versions were compared, the most appropriate translated version was considered. The Armenian version of the questionnaire content consistency was reviewed by second year Masters of Public Health program’s students at AUA who are Armenian native speakers. The translated Armenian version of the self-administered survey questionnaire will be pretested among ten participants. The pretest will be conducted among the patients who visited family physicians in a selected polyclinic.

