3.3.4 Variables

The dependent variable of interest is Patient-Physician Relationship percent score, which is a numerical continuous outcome variable (Table 2). It is measured through 25 questions. The response options for each statement consists of nine levels of agreement between “Strongly Disagree” to “Strongly Agree”. The patient-physician relationship score ranging from 25-225 from the questionnaire will be re-calculated to patient-physician relationship percent score ranging from 11% to 100%.

The main independent variable of interest is being from Heratsi (intervention) or Muratsan (comparison) polyclinics. It is a nominal dichotomous type of variable. The special identification number of the questionnaire will identify the information.

The control variables suggested by literature include: participant’s sex, age, socio-economic status, educational status, and marital status.^{31,35,38,39} Literature shows that the above-mentioned control variables can influence the desired outcome of variable.^{31,35,38,39}

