6.1 Human Subject

For the evaluation process, family physicians' patients are the participants of the survey. The instrument is a self-administrated survey questionnaire. The participants are human subjects, age over eighteen years and under sixty-five years old. The participation in the survey is voluntary, and the survey participants can refuse to answer any questions or quit completing the questionnaire at any point in time. The American University of Armenia Institutional Review Board reviewed and approved the study protocol.

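### The training acts on physicians, but the sample size and tests ignore physician clustering and no physician is recorded, so follow-up comparisons between polyclinics will have standard errors that are too small

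*Protocol*

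**What the plan says.** **Who is trained.** Section 3.2.1: "We proposed to implement the Physician Leadership Development Program to the family physicians of Heratsi polyclinic".

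**Who is measured.** Section 6.1: "For the evaluation process, family physicians' patients are the participants of the survey". In Appendix 3, items 3 to 27 form the score, and items 7 to 27 all refer to the respondent's doctor.

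**Analysis.** Section 3.3.5: "Analysis will include descriptive analysis, independent T-test for continuous variables", followed by chi-square tests and bivariate and multivariate linear regression. The covariates are patient characteristics only (Section 3.3.4): "The control variables suggested by literature include: participant’s sex, age, socio-economic status, educational status, and marital status". Neither that section nor Table 2 has a physician variable.

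**Sample size.** Section 3.3.3.1 uses the plain two-means formula with a 95% response rate, and no intracluster correlation, cluster size or design effect.

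**Identifier.** Section 3.3.3 Questionnaire: "The special identification number will consist of six characters". The first is H or M ("Latter is to represent the polyclinic where the survey participant took the survey"), the second is the assessment wave, and the rest is a serial number: "The other four characters of the identification number will feature Arabic numbers, which will be the numbers of the survey participant". The form adds a date. No item asks which physician was seen, and no log linking form to physician is described.

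**The concern.** A patient's score depends partly on which physician was seen. If physicians differ, two patients of the same physician resemble each other more than two patients of different physicians, and 1,198 questionnaires carry less information than 1,198 independent ones. A t-test or ordinary regression that ignores this gives standard errors that are too small when two polyclinics, each with its own set of physicians, are compared.

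Two stated targets are comparisons of that kind: the success criterion in Section 3.3.3.1 (intervention against comparison at the first follow-up) and the third objective in Section 3.3.1 (intervention against comparison in June 2016). At stake is a false claim of success.

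A model can usually be left to the analysis plan. Here the protocol fixes the data items, and the one item that a clustered model needs is absent.

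**Working it through.** **1. The plan's own sample size.** The printed formula is n = (1.96 + 1.28)² × (2.5² + 2.5²) / 0.585² = 10.4976 × 12.5 / 0.3422 = 383.4, so 384 per group, not 1,198. The figure 1,198 appears if the two variances are multiplied instead of added: 10.4976 × 39.0625 / 0.3422 = 1,198.2. The step to 1,262 reproduces (1,198 / 0.95 = 1,261.05, rounded up). No step contains a cluster term.

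**2. Which n to use.** The protocol supports three values per group and wave:
- 1,198, as stated.
- 384, from the printed formula.
- 180, from Section 3.3.3.2. Dividing daily visitors by nine yields nine respondents a day, and 9 × 20 days = 180. The same section asks for 64 a day. The data-entry footnote in Appendix 6 counts 1,080 questionnaires, which is 180 × 6 surveys.

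**3. Assumed inputs.** The number of physicians is not stated. The only hint is in Section 5: "the classroom of 18 seating capacity is considered as an optimal", with two cohorts in Section 3.2.1. I take 18 to 36 physicians (k) per polyclinic. The intracluster correlation (ICC) is not stated; I take 0.01, 0.05 and 0.10.

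**4. Between-polyclinic comparison at one follow-up.** With m = n/k patients per physician:
- design effect DE = 1 + (m − 1) × ICC
- real two-sided error of the nominal 5% test = 2 × [1 − Φ(1.96/√DE)]

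Example with n = 1,198, k = 18, ICC 0.05: m = 66.6; DE = 1 + 65.6 × 0.05 = 4.28; effective n = 1,198 / 4.28 = 280; 1.96/√4.28 = 0.95; error 34%.

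| n per group | k | DE at ICC 0.01 / 0.05 / 0.10 | Real error |
|---|---|---|---|
| 1,198 | 36 | 1.32 / 2.61 / 4.23 | 9% / 23% / 34% |
| 1,198 | 18 | 1.66 / 4.28 / 7.56 | 13% / 34% / 48% |
| 384 | 36 | 1.10 / 1.48 / 1.97 | 6% / 11% / 16% |
| 384 | 18 | 1.20 / 2.02 / 3.03 | 7% / 17% / 26% |
| 180 | 36 | 1.04 / 1.20 / 1.40 | 5.5% / 7.4% / 9.8% |
| 180 | 18 | 1.09 / 1.45 / 1.90 | 6.0% / 10.4% / 15.5% |

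More patients per physician make the error worse, so the large stated sample gives no protection.

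**5. Before–after comparison within the intervention polyclinic (first two objectives in Section 3.3.1).** Suppose the same physicians are seen in the same proportions at both waves. Split the ICC into a stable part ρs and a physician-by-wave part ρw. The true variance of the difference, divided by the naive variance, is (1 − ρs − ρw) + m × ρw.
- All stable (ρw = 0): the ratio is 0.99, 0.95 or 0.90, and the error is 4.9%, 4.4% or 3.9%. There is no inflation.
- Half of an ICC of 0.05 varying by wave, k = 18, n = 1,198: 0.95 + 66.6 × 0.025 = 2.61, and the error is about 23%.

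Inflation here depends wholly on ρw, on which the protocol gives nothing.

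**The case against.** **The size is uncertain.** The ICC and physician numbers are assumptions, and a seat count is not a head count. The 9–48% range belongs to the largest of three sample sizes that the protocol supports. This stands, so all three are shown.

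**The score is only partly about the doctor.** Ten items (8–12 and 23–27) describe the doctor; the other 15 describe the patient's own attitudes or conduct, although 11 of those still refer to the doctor. This may lower the ICC of the total score and makes 0.10 a less obvious value. It does not make the ICC zero.

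**Most objectives are before–after.** Two of three are. A reader might infer that every planned test exceeds 5%. The documents do not support that: with stable physician effects the before–after tests hold their level.

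**Physicians could be treated as fixed.** Stable physician differences are then not sampling error but part of the non-equivalence of the two polyclinics, which the design section already names as selection bias. That is a coherent narrower reading. It makes no claim beyond these particular physicians, and the plan does not state it.

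**The analysis plan could handle it.** The term for a two-sample t-test is not itself a fault, and regression standard errors are often specified later. But a physician term cannot be fitted to data that were not collected. A reader might go further and infer that nothing at all could be done. That is too strong: a sensitivity analysis over assumed ICCs remains possible, and the form date with the even/odd-day rota gives a coarse grouping. Neither replaces a physician identifier.

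**Trained against untrained physicians.** One might infer that the missing code also blocks this comparison at Heratsi. The protocol describes no untrained subgroup there, so the point does not rest on it.

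**Conclusion.** The concern holds for the between-polyclinic comparisons at follow-up. Patients are analysed and counted as independent, the intervention acts on physicians, and the form as specified rules out a physician-clustered analysis. Over ICC 0.01–0.10 and 18–36 physicians per polyclinic, the real error of a nominal 5% test is about 9–48% at 1,198 per group, 6–26% at 384 and 5.5–15.5% at 180. For the before–after objectives, inflation arises only if physician effects change between waves.

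The harm is false positives and intervals that are too narrow. A reader might also infer a general loss of power. For the 8.36-point difference in the text (64.07 − 55.71) with SD 2.5, power stays near 1 throughout. For the 0.585 used in the formula, a cluster-adjusted test at 1,198 with 18 physicians has power of about 0.79 at ICC 0.05 and 0.55 at ICC 0.10.

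Nor would a physician code yield a clean programme effect. With one polyclinic per arm, programme and polyclinic remain confounded.

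**What to change.** - **Before the August 2015 baseline**, add a non-identifying physician code to the questionnaire ID (two further characters would do). The supporting staff, who already approach patients after the visit, enter it at exit.
- **Analysis.** Analyse the score by a linear mixed model with physician and physician-by-wave random effects, or by regression with physician-clustered standard errors and a small-sample correction. Use this in place of the plain t-test and ordinary regression for the outcome. Report the ICC from the baseline wave.
- **Sample size.** State the number of physicians per polyclinic and an assumed ICC, and carry the design effect through the calculation once its arithmetic and the daily quota are reconciled.
- **Interpretation.** State that the model corrects the physician-level standard error but does not separate programme from polyclinic effects.

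**Cost.** Intervals will be wider. The form change is small but probably needs an ethics amendment, since the protocol is already approved. Physicians who know that ratings are coded to them may react more strongly, a threat that the design section already names. Waiting costs more: a baseline collected without the code cannot be recovered.

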6.1 Human Subject

For the evaluation process, family physicians' patients are the participants of the survey. The instrument is a self-administrated survey questionnaire. The participants are human subjects, age over eighteen years and under sixty-five years old. The participation in the survey is voluntary, and the survey participants can refuse to answer any questions or quit completing the questionnaire at any point in time. The American University of Armenia Institutional Review Board reviewed and approved the study protocol.

Baseline Assessment (O₀) August 2015	
 a) Patients registered with Heratsi or Muratsan polyclinics b) Patients over the age of eighteen years old and under sixty five years old c) Patients visiting family physicians 	
Additional Criteria for the Follow-up Assessment (O₁) December 2015		
 a) Patients who registered with these polyclinics after August 2015 b) Patients who participated in the baseline assessment (O₀)
Additional Criteria for the Follow-up Assessment (O₂) June 2016		
 a) Patients who registered with these polyclinics after August 2015 b) Patients who participated in the baseline assessment (O₀) and the follow-up assessment (O₁)

Table 2: Variables and Sources of Data

Variables	Type	Measure	Sources
Dependent Variable Patient-Physician Relationship percent score	Numerical (Continuous)	Percent score (Minimum – 11% Maximum – 100%)	Self-administered questionnaire
Independent Variable Patients being from Intervention or Comparison polyclinics	Nominal (Dichotomous)	Patients of Family Physician from Heratsi or Muratsan	Self-administered questionnaire
Control Variables			
Age	Numeric (Continuous)	Age in Years	Self-administered questionnaire
Sex	Nominal (Dichotomous)	“Male” Or “Female.”	Self-administered questionnaire
Marital Status	Nominal	1) Single 2) Married 3) Widowed 4) Divorced	Self-administered questionnaire
Social-economic Status	Ordinal	1) Less than 50,000 drams 2) From 50,001 - 100,000 drams 3) From 100,001 - 200,000 drams 4) From 200,001 - 300,000 drams 5) Above 300,000 drams	Self-administered questionnaire
Educational Status	Ordinal	1) Incomplete secondary (less than 10 years) 2) School (10 years) 3) Professional technical (10-13) 4) Institute/University 5) Post-graduate	Self-administered questionnaire

Appendix 1: WHO's Conceptual Framework on Health Systems

Appendix 2: Program Curriculum Guide

Physician Leadership Development Program

Curriculum Guide

Unit - Physician Leadership Development Program

Educator - Physicians with MPH degree, who underwent training of trainers (TOT) course

Participants - Family physicians from primary healthcare centers

Settings - The classes will be conducted in classrooms at American University of Armenia

Goal - To develop leadership skills for implementing in the healthcare settings in terms of

- Demonstrating personal qualities,
- Working with others,
- Managing services,
- Improving Services,
- Setting direction.

Competency/Objectives - By the end of the program the family physicians will be able to:

- Understand the significance of personal qualities and apply them in terms of acting with integrity,
- Employ the skills of building relationships and encouraging contribution,
- Use the skills of planning and managing resources, people and performance,
- Promote to innovation and apply the skills of critical evaluation,
- Analyze knowledge and evidence to making decisions and evaluating impact.

Teaching Techniques

- Delivering interactive lectures,
- Initiating group/pair discussions among the family physicians,
- Demonstrating videos for analyzing cases,
- Organizing debates,
- Providing real scenarios for solving problems
- Delivering worksheets for matching, gap-filling and open-ended exercises,
- Doing self-assessment.

Package to the participants - Pens, lecture notes, notebooks.

Package to the educator - Lecture notes, board, markers, projector, and loudspeakers.

Introduction Session

Introduction to the Edward Jenner Programme: Leadership Foundations

Description

Working in a new healthcare role can be challenging, however, we know that with the right support and guidance clinicians can feel better equipped to care for patients and to lead healthcare services. High quality, safe patient care is of primary importance. Patients recognize and value compassionate care and the vital role that clinicians like you offer them. They appreciate that clinicians need to continually learn in order to improve services for patients.

The Edward Jenner programme aims to improve the confidence and competence of clinicians as well as improving the quality and safety of patient care. Throughout this programme, there are opportunities for you to reflect on your experiences so that you can use this learning as part of your continuing professional development.

Module 1. Session 1

Demonstrating Personal Qualities: Developing Self-awareness

Description

This session will discuss the importance of developing self-awareness in healthcare and ways to enhance your own self-awareness in your practice to further your development.

Learning Objectives

This session will support you to:

- Recognize and articulate your own values and principles, understanding how these may differ from those of other individuals and groups
- Identify your own strengths and limitations, the impact of your behavior on others, and the effect of stress on your behavior
- Identify your own emotions and prejudices and understand how these may affect your judgment and behavior
- Obtain, analyze and act on feedback from a variety of sources

Module 1. Session 2

1.2 Demonstrating Personal Qualities: Managing Yourself

Description

This session will explore organizing and managing yourself whilst taking account of the needs and priorities of others.

Learning Objectives

This session will support you to:

- Manage the impact of your emotions on your behavior with consideration of the impact on others
- Be reliable in meeting your responsibilities and commitments to consistently high standards
- Ensure that your plans and actions are flexible, and take account of the needs and work patterns of others
- Plan your own workload and activities to fulfil work requirements and commitments, without compromising your health

Module 1. Session 3

1.3 Demonstrating Personal Qualities: Continuing Personal Development

Description

Embracing lifelong learning as a dynamic process that can positively influence practice and healthcare is an essential aspect of on-going development for all professions involved in healthcare.

Learning Objectives

This session will support you to:

- Actively seek opportunities and challenges for personal learning and development
- Acknowledge mistakes and treat them as learning opportunities
- Participate in continuing professional development activities
- Change your behavior in the light of feedback and reflection

Module 1. Session 4.

1.4 Demonstrating Personal Qualities: Acting with Integrity

Description

This session will encourage you to further explore acting with integrity, behaving in an open, honest and ethical manner, as a healthcare practitioner.

Learning Objectives

This session will support you to:

- Uphold personal and professional ethics and values, taking into account the values of the organization and respecting the culture, beliefs and abilities of individuals
- Communicate effectively with individuals, appreciating their social, cultural, religious and ethnic backgrounds and their age, gender and abilities
- Value, respect and promote equality and diversity
- Take appropriate action if ethics and values are compromised

Module 2. Session 1

